1. OBJECTIVES

The objective of this phase 2 study is to determine the antitumor activity of the CTLA-4 inhibitor tremelimumab in combination with the PD-L1 inhibitor durvalumab (MEDI4736) in malignant pleural mesothelioma. Immunologic and genomic biomarkers of response will also be evaluated through correlative studies incorporated throughout this trial.

1.1 Study Design

This is an open-label, single-arm, phase 2 study of tremelimumab plus durvalumab in patients with previously-treated unresectable malignant pleural mesothelioma.

1.2 Primary Objective

• Examine the overall response rate (ORR) utilizing modified RECIST criteria for mesothelioma

1.3 Secondary Objectives

- Determine the progression free survival (PFS) rate, defined as the time from registration to disease progression or death due to any cause. Participants alive without disease progression will be censored at date of last disease evaluation.
- Determine the overall survival (OS) rate, defined as the time from registration to death due to any cause (or censored at date last known alive).
- Determine the duration of response (DoR), defined as the time from documentation of tumor response to disease progression (or censored at the date of last disease evaluation).
- Evaluate the safety and tolerability of tremelimumab in combination with durvalumab.

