5.7 Duration of Follow Up

Participants will be followed until death after removal from protocol therapy. This follow up will be performed by review of the medical record, contact with care providers, and/or telephone contact as needed every 3-4 months.

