11.1.4.4 Evaluation of Best Overall Response

The best overall response is the best response recorded from the start of the treatment until disease progression/recurrence (taking as reference for progressive disease the smallest measurements recorded since the treatment started). The patient's best response assignment will depend on the achievement of both measurement and confirmation criteria.

For Participants with Measurable Disease (*i.e.*, Target Disease)

Table 8: Criteria for Participants with Measurable Disease									
Target Lesions	Non-Target Lesions	New Lesions	Overall Response	Best Overall Response when Confirmation is Required					
CR	CR	No	CR	≥4 wks Confirmation*					
CR	Non-CR/Non- PD	No	PR						
CR	Not evaluated	No	PR	>4 wks Confirmation**					
PR	Non-CR/Non- PD/not evaluated	No	PR						
SD	Non-CR/Non- PD/not evaluated	No	SD	Documented at least once ≥4 wks from baseline**					
PD	Any	Yes or No	PD						
Any	PD***	Yes or No	PD	no prior SD, PR or CR					
Any	Any	Yes	PD]					

* Only for non-randomized trials with response as primary endpoint.

** In exceptional circumstances, unequivocal progression in non-target lesions may be accepted as disease progression.

Note: Participants with a global deterioration of health status requiring discontinuation of treatment without objective evidence of disease progression at that time should be reported as "*symptomatic deterioration*." Every effort should be made to document the objective progression even after discontinuation of treatment.

For Participants with Non-Measurable Disease (i.e., Non-Target Disease)

Table 9: Criteria for Participants with Non-Measurable Disease							
Non-Target Lesions	New Lesions	Overall Response					
CR	No	CR					
Non-CR/non-PD	No	Non-CR/non-PD*					
Not all evaluated	No	not evaluated					
Unequivocal PD	Yes or No	PD					
Any	Yes	PD					
* 'Non-CR/non-PD' is preferred over 'stable disease' for non-target disease since SD is							

increasingly used as an endpoint for assessment of efficacy in some trials so to assign this category when no lesions can be measured is not advised

11.1.5 Duration of Response

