Duration of overall response: The duration of overall response is measured from the time measurement criteria are met for CR or PR (whichever is first recorded) until the first date that recurrent or progressive disease is objectively documented (taking as reference for progressive disease the smallest measurements recorded since the treatment started, or death due to any cause. Participants without events reported are censored at the last disease evaluation).

Duration of overall complete response: The duration of overall CR is measured from the time measurement criteria are first met for CR until the first date that progressive disease is objectively documented, or death due to any cause. Participants without events reported are censored at the last disease evaluation.

Duration of stable disease: Stable disease is measured from the start of the treatment until the criteria for progression are met, taking as reference the smallest measurements recorded since the treatment started, including the baseline measurements.

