13.1 Study Design/Endpoints

Primary Efficacy Measure:

• Investigate the ORR in patients with malignant pleural mesothelioma.

Secondary Efficacy Measures:

- Evaluate the safety and tolerability of tremelimumab in combination with durvalumab.
- Determine the OS, PFS, and DoR in patients with malignant pleural mesothelioma.

Exploratory Endpoints:

- Investigate the immunologic determinants of primary response and resistance to tremelimumab in combination with durvalumab in malignant pleural mesothelioma
- Investigate the immunologic mechanisms of acquired resistance to tremelimumab in

combination with durvalumab

• Investigate genomic correlates of response to tremelimumab in combination with durvalumab

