13.3 Analysis of Primary and Secondary Endpoints

The primary and secondary analyses will include all eligible patients who started assigned therapy. The exception to this includes the planned analysis of toxicity data, which will include all patients who received study drug regardless of eligibility. Response will be assessed using the modified RECIST criteria for mesothelioma; toxicity will be graded using CTCAE v. 4.03.

For the analysis of the response efficacy measures, participants will be censored if they are alive and without disease progression at the date of the last disease evaluation. In the case of OS, participants will be censored if they are living at the date last known alive.

Time-to-event data, such as PFS and OS, will be estimated using the Kaplan-Meier method, and Cox proportional hazards models will be used to estimate hazard ratios. Comparisons of groups will be made using the logrank test and Cox modeling.

Categorical data, such as response rates (CR+PR) and toxicity, will be compared using Fisher's exact tests with a one-sided type I error rate of 10%; multivariable logistic regression modeling will be used to adjust for the effect of any covariates that are associated with these categorical outcomes. Though none are currently planned, any continuous outcomes will be analyzed using Wilcoxon rank sum test, and multivariable linear regression models may be used to adjust for multiple associations with outcome.

Modeling procedures will implement backward selection; variables significant at the 0.10 level in the univariate setting will be chosen for inclusion in an initial full model, and at each step the least significant variable will be removed from the model. Only those covariates with p<0.05 will remain in any final models, unless there are factors identified by the study team as crucial to model interpretation.

Point estimates of all endpoints will be accompanied by the corresponding two-sided 80% confidence intervals. The method of Atkinson and Brown will be used for the estimation of the confidence interval for response.

In the event that there are missing data, no imputation of the missing data will be conducted. We will assume that data are missing at random and will conduct all analyses as originally planned because we do not anticipate an excess of missing data.

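### Section 1.3 leaves death out of the duration-of-response definition, contradicting Section 11.1.5, which counts it

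*Combined protocol and SAP*

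**What the plan says.** DoR is a secondary efficacy measure. Section 13.1 lists it without defining it: "Determine the OS, PFS, and DoR in patients with malignant pleural mesothelioma".

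Section 1.3 supplies one definition: "defined as the time from documentation of tumor response to disease progression (or censored at the date of last disease evaluation". The PFS bullet in the same list names death as an event and restricts censoring: "Participants alive without disease progression will be censored at date of last disease evaluation".

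Section 11.1.5 supplies another. Duration of overall response runs from first CR or PR "until the first date that recurrent or progressive disease is objectively documented", and the definition closes with "or death due to any cause. Participants without events reported are censored at the last disease evaluation". Duration of complete response, defined next, also ends at progression or death.

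Section 13.3 gives the censoring rule for the response efficacy measures: "participants will be censored if they are alive and without disease progression at the date of the last disease evaluation". It does not name DoR.

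**The concern.** Under Section 1.3 the only event is progression, and everyone else is censored at the last disease evaluation. A responder who dies without documented progression is then handled as though the response were still running when last seen. That censoring is informative, because the response ended in death. Under Section 11.1.5 the same death is an event.

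Section 13 does not define DoR, so the analyst would have to choose between the two definitions. In an open-label, single-arm trial that choice should be fixed before the data are seen.

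Such deaths are plausible, although the documents give no rate. In the NSCLC study of this combination described in Section 2.4.2, 26 of 102 subjects (25.5%) stopped treatment because of serious adverse events. Section 5.7 describes follow-up after treatment by record review, provider contact or telephone, and mentions no imaging. A responder who stops for toxicity could therefore die with no scan showing progression. Against this, Section 11.1.4.4 says "Every effort should be made to document the objective progression even after discontinuation of treatment". That note was written for symptomatic deterioration, but it may limit the number of cases.

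**Working it through.** The plan states no DoR figure to reproduce, so the check is a comparison of the texts followed by an illustration of size.

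**Step 1. The texts side by side**

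| Place | What ends the interval | Who is censored | Responder who dies without documented progression |
|---|---|---|---|
| 1.3, DoR | Progression | Everyone else, at last evaluation | Censored |
| 1.3, PFS (comparison) | Progression or death | Alive and progression-free | Event |
| 11.1.5, overall response | Recurrence, progression or death | No event reported | Event |
| 11.1.5, complete response | Progression or death | No event reported | Event |
| 13.3, response measures | Not listed | Alive and progression-free | Not within the censoring rule |

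Only the Section 1.3 DoR bullet censors this responder. In the overall-response definition of Section 11.1.5, a bracket opened for the reference measurement closes only after the censoring sentence. The death event and the censoring rule therefore both sit inside it. Death makes sense there only as an end event, and the complete-response definition, which is cleanly punctuated, confirms this.

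**Step 2. Kaplan-Meier illustration**

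Inputs: 0.35 × 40 = 14 responders, from the target rate and sample size in Section 13. The DoR-ending times of 2, 4, ..., 28 months are assumed, and all are observed. S(t) is the product of (1 − events/number at risk), and the median is the first time S(t) ≤ 0.5. Under 1.3, deaths are censored at the last scan.

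- Section 11.1.5, all 14 are events: S(12) = 8/14 = 0.571; S(14) = 7/14 = 0.500; median 14 months.
- (a) Section 1.3, one death at month 8, last scan at 7: S(6) = 11/14, then 10 at risk. S(12) = 11/14 × 8/10 = 0.629; S(14) = 11/14 × 7/10 = 0.550; S(16) = 11/14 × 6/10 = 0.471; median 16.
- (b) Section 1.3, deaths at 6 and 10, last scans at 5 and 9: S(12) = 12/14 × 10/11 × 8/9 = 0.693; S(16) = 12/14 × 10/11 × 6/9 = 0.519; S(18) = 12/14 × 10/11 × 5/9 = 0.433; median 18.
- (c) Section 1.3, deaths at 24 and 26, last scans at 23 and 25: nothing changes before month 23; S(12) = 0.571; median 14.
- (d) Section 1.3, deaths at 24 and 26, both last scanned at month 1: 12 at risk from month 2; S(12) = 6/12 = 0.500; median 12.

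A check with 10 responders (assumed times 4, 6, ..., 22) shows the same pattern. The 11.1.5 median is 12. Under 1.3 it is 14 with one death at 8 (scan at 7), and 10 with deaths at 18 and 20 (both last scanned at 3).

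**Step 3. Constant-hazard approximation**

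Let s be the share of DoR-ending events that are deaths without documented progression (assumed). The all-event hazard is λ and the progression hazard is λ(1 − s). The ratio of medians, deaths censored over deaths counted, is [ln 2 / (λ(1 − s))] / [ln 2 / λ] = 1/(1 − s). For s = 0.10, 0.20 and 0.30 this gives 1.11, 1.25 and 1.43. The formula censors at the time of death. Section 1.3 censors at the earlier scan, so this is a guide only.

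**The case against.** The strongest objection concerns Section 13.3. It says participants are censored if alive and progression-free, without the word only, and it does not name DoR. Its closing date phrase could also describe the participant's status at the last scan instead of the censoring date. On that reading, a responder who was well at the last scan and died later would be censored, as in Section 1.3. The omission of DoR stands. The alternative reading is weak: the next sentence deals separately with OS, so the rule covers the other measures, and censoring later deaths would contradict the PFS definitions in Sections 1.3 and 11.1.6. Even without Section 13.3, Section 1.3 is at odds with both duration definitions in 11.1.5 and with its own PFS bullet.

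Second, no order of precedence is stated, and Section 11.1 carries generic text (for example, randomization in a single-arm trial). Preferring 11.1.5 is therefore a judgement. That is true, but 11.1.5 is the fuller operational definition and agrees with the rest of the plan.

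Third, the illustration is stylised. At 5 patients per quarter, 40 patients take 8 quarters. With up to one further year, late responders would be censored well before 28 months. Scenario (d) needs scan gaps of 23 and 25 months, against a schedule of one scan every 8 weeks. These points stand: the figures show direction and sensitivity and are not forecasts.

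Finally, DoR has no hypothesis test or decision rule attached. That limits the weight of the point but does not remove the contradiction.

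**Conclusion.** The concern holds. Two current sections give opposite treatment to a responder who dies without documented progression, and following Section 1.3 as written would distort the DoR curve whenever such a death affects it.

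The size is unknown, and it is zero if there are no such deaths. In the 14-responder illustration the median moves from 14 months to between 12 and 18, depending on how many such deaths occur, when they occur and how old the last scan is. All event times, and the share s, are assumptions. The usual direction is a longer apparent DoR. A downward shift needs very old last scans.

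This should be corrected, but it does not threaten the main result: DoR does not enter the response rate, the two-stage boundaries, type I error or power.

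**What to change.** Three wording edits:

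1. In Section 1.3, define DoR as in Section 11.1.5: time from the first documented CR or PR to progression or death from any cause, whichever comes first. Censor only participants alive and progression-free, at the last disease evaluation.
2. In Section 13.3, name DoR in the censoring sentence. The same edit can make clear that the last disease evaluation is the censoring date.
3. In Section 11.1.5, close the bracket directly after the reference-measurement phrase, so that death and the censoring rule stand outside it.

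Data collection, sample size and the primary analysis do not change. Section 5.7 already provides the deaths: "Participants will be followed until death after removal from protocol therapy". The cost is that the reported median DoR may be shorter than under the Section 1.3 wording, by an amount that depends on how many responders die without documented progression and when they were last scanned.

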1.4 Exploratory Objectives

- Investigate the immunologic determinants of primary response and resistance to tremelimumab in combination with durvalumab in malignant pleural mesothelioma
- Investigate the immunologic mechanisms of acquired resistance to tremelimumab in combination with durvalumab
- Investigate genomic correlates of response to tremelimumab in combination with durvalumab

2. BACKGROUND

2.1 Study Disease

Malignant mesothelioma is an insidious cancer with a very poor prognosis. There are about 3300 new cases of mesothelioma diagnosed in the United States each year, and 80% of these cases are pleural in origin. Mesothelioma results in significant morbidity and mortality typically through local invasion, and patients often experience progressive chest pain, shortness of breath, fatigue,

and hypoxemia related to encasement of the lungs and accumulation of pleural fluid. Extension into other thoracic structures can cause a number of disabling symptoms including dysphagia, spinal cord and brachial plexus injury, superior vena cava syndrome, and cardiac dysfunction.

For patients with unresectable pleural mesothelioma, cisplatin-pemetrexed is the only FDAapproved treatment regimen based on a 2003 randomized phase III first-line trial comparing this combination with cisplatin monotherapy.¹ In this study, chemotherapy-naïve patients who received cisplatin and pemetrexed had a significantly longer median survival time (12.1 vs. 9.3 months) and higher response rates (41.3% vs. 16.7%) compared to those receiving cisplatin alone. There are no effective second-line treatment options for patients with mesothelioma. There was a 16% response to weekly vinorelbine in a single-arm phase II trial of 63 patients with relapsed mesothelioma.² A retrospective study of 66 mesothelioma patients treated with secondor third-line vinorelbine or gemcitabine found the response rate to be only 2%.³

Immune checkpoint blockade as monotherapy was recently evaluated in a randomized, doubleblind, placebo-controlled study of tremelimumab in patients with unresectable pleural or peritoneal mesothelioma (Study D4880C0003, NCT01843374) and unfortunately was found not to extend overall survival. However, in the Keynote-028 phase Ib trial of patients with advanced solid tumors, among 25 PD-L1 positive mesothelioma patients treated with pembrolizumab, a partial response was seen in 7 patients and stable disease was seen in 12 patients⁴. In support of this finding is a growing body of evidence that a substantial number of malignant mesotheliomas express the immune checkpoint marker PD-L1. In one recent study of 106 mesothelioma cases, PD-L1 was detected in 40% of patients by immunohistochemistry (IHC). Furthermore, nearly all samples with sarcomatoid histology expressed PD-L1. Compared to PD-L1-negative specimens, expression of PD-L1 was associated with a significant decrease in median overall survival (5 months vs. 14.5 months).⁵

Recent pre-clinical work has suggested that targeting both PD-L1 and CTLA-4 may have additive or synergistic effects⁶. Based on these results, we hypothesize that PD-L1 inhibition with durvalumab and CTLA-4 inhibition with tremelimumab will result in high response rates in previously-treated patients with malignant pleural mesothelioma.

2.2 Durvalumab

Durvalumab is a human monoclonal antibody (mAb) of the immunoglobulin G (IgG) 1 kappa subclass that inhibits binding of PD-L1 and is being developed by AstraZeneca/MedImmune for use in the treatment of cancer. As durvalumab is an engineered mAb, it does not induce antibody-dependent cellular cytotoxicity or complement-dependent cytotoxicity. The proposed mechanism of action for durvalumab is interference of the interaction of PD-L1.

PD-L1 is expressed in a broad range of cancers with a high frequency, up to 88% in some types. In a number of these cancers, including lung, the expression of PD-L1 is associated with reduced survival and an unfavorable prognosis. In lung cancer, only 12% of patients with tumors expressing PD-L1 survived for more than 3 years, compared with 20% of patients with tumors lacking PD-L1⁷. Based on these findings, an anti-PD-L1 antibody could be used therapeutically

to enhance anti-tumor immune responses in patients with cancer. Results of several non-clinical studies using mouse tumor models support this hypothesis, where antibodies directed against PD-L1 or its receptor PD-1 showed anti-tumor activity⁸⁻¹⁰.

2.2.1 Summary of Durvalumab Pre-Clinical Studies

Engagement of PD-1 on T cells inhibits activation with downstream effects on cytokine production, proliferation, cell survival, and transcription factors associated with effector T-cell function¹¹⁻¹⁶.

Durvalumab has shown the following activity as an anti-PD-L1 molecule:

- Durvalumab binds to PD-L1 and blocks its interaction with PD-1 and CD80
- Durvalumab can relieve PD-L1-mediated suppression of human T-cell activation in vitro
- Durvalumab inhibits tumor growth in a xenograft model via a T-cell dependent mechanism
- A surrogate anti-mouse PD-L1 antibody resulted in improved survival in a syngeneic tumor model as monotherapy and resulted in complete tumor regression in > 50% of treated mice when given in combination with chemotherapy
- In the same study, anti-mouse PD-L1 antibody-treated mice were completely tumor free 3 months after tumor implantation and demonstrated long-term immunity during rechallenge
- In a subsequent study in the same syngeneic model, the combination of an anti-mouse PD-L1 antibody and anti-CTLA-4 antibody resulted in complete tumor regression in all mice treated

The cynomolgus monkey is considered to be the only relevant nonclinical species for evaluation of local and systemic toxicities of durvalumab. In addition, *in vivo* in cynomolgus monkeys, durvalumab suppresses soluble PD-L1 (sPD-L1) in serum and fully occupies membrane PD-L1 on various leukocyte subsets at doses equal to or more than 0.1 mg/kg (lowest dose tested) with a dose-related duration of suppression and occupancy.

In general, there were no durvalumab-related adverse effects in toxicity studies conducted in cynomolgus monkeys with durvalumab considered to be of relevance to humans. Adverse findings in the non-Good Laboratory Practice (GLP) pharmacokinetic (PK)/pharmacodynamic and dose range-finding study (4 doses over 5 weeks), and a GLP 4-week repeat-dose toxicity study were consistent with anti-drug antibody (ADA)-associated morbidity and mortality in individual animals. The death of a single animal in the non-GLP, PK/pharmacodynamic, and dose range-finding study was consistent with an ADA-associated acute anaphylactic reaction based on the presence of ADAs within days of the first dose, acuteness and timing (after repeated dosing) of the death, clinical signs consistent with an anaphylactic reaction, lack of remarkable effects on other study parameters, and lack of histopathologic findings consistent with any other cause of death. In addition, the spectrum of findings, especially the clinical signs and microscopic pathology, in a single animal in the GLP, 4-week, repeat-dose study was consistent with ADA-associated immune complex deposition. Similar effects have been observed by MedImmune in cynomolgus monkeys administered other unrelated human MAbs. With durvalumab, ADA immune-complexes were identified in the affected animal in a subsequent

investigative immunohistochemistry study. Given that immunogenicity of human MAbs in nonclinical species is not generally predictive of responses in humans, the ADA-associated morbidity and mortality were not taken into consideration for the determination of the noobserved-adverse-effect level (NOAEL) of durvalumab in these studies. Finally, interim audited data from the dosing phase of the pivotal 3-month, repeat-dose GLP toxicity study in cynomolgus monkeys, showed that subchronic dosing of durvalumab was not associated with any adverse effects. Therefore, the NOAEL of durvalumab in all the general toxicity studies was considered to be 100 mg/kg, the highest dose tested in these studies.

